## **8 STUDY PROCEDURES**

### **8.1 Study Flow Chart/Table of Study Procedures and Assessments**

Flow-chart see chapter 5.2.

[figure not shown]
**Study plan:** Effects of photodynamic therapy on the human inguinal skin microbiome to improve antiseptic effect

Study tasks	Screening	Intervention Period			Follow-up
		1	2	3	
Visits					
	at least -7	0	7±3	21±7	35±7
7. Participant information and informed consent	√				
8. Inclusion- and exclusion criteria	√				
9. Demographic data	√				
10. Inguinal skin scraping before photodynamic treatment		√			
11. Natural bacterial porphyrin fluorescence photography		√	√	√	√
12. Study intervention: Photosensititer application, followed by fluorescence photography Photodynamic therapy (PHT) (1x) over 15 minutes at the dermatology ward		√			
13. Primary outcome measure: Skin antisepsis in the groin, skin scraping after antisepsis		√			
14. Secondary outcome measure: Punch biopsy  specimen of the MAL-PDT area (immediately after PDT) and of an untreated area as a control		√		√	
15. Primary and secondary outcome measure: Inguinal skin scraping and punch biopsy  of the MAL-PDT area			√	√	
16. (serious) adverse events			√	√	√
17. End of study information of study results					√

 optional, only in 5 volunteers

## Skin scrapping

For all skin swabs, we will apply the scratching method using a scalpel as described previously (17) and illustrated below in Figure 2. The swabs and the biopsies will be analyzed for bacterial growth. The remaining sample will be immediately frozen at -80C° for later molecular analysis such as metagenomics.

**Figure 2.** Specimen collection in the groin of the hip before disinfection. Skin scrapings will be removed with sterile blades and transferred to ESwab culture swabs (Copan).  
T, musculus tensor fascia latae; Tr, trochanter

## Photodynamic treatment

This will be done by the dermatologist Dr. med. [name]. She will apply 5% topical methyl aminolevulinate (MAL) as the photosensitizer for 3 hours under occlusion in the right groin of the participant. She will then start the photodynamic process by irradiation of the area with 40J/cm^2 red light from a 633 nm emitting LED during 13 minutes.

## Skin antisepsis

After the MAL- photodynamic treatment, we will perform skin antisepsis as routinely done in clinics three times with a povidone-iodine/alcohol solution (Betaseptic®, Mundipharma, Limburg, Germany) for a total duration of 3 minutes to imitate standard surgical antisepsis before a hip arthroplasty surgery. We will perform skin scraping (see above) before and after the 3rd antisepsis and 21 days later for bacterial cultures.

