## 4 STUDY OUTCOMES

### 4.1 Primary Outcome

**Outcome 1:** Immediate effect (Same day) of photodynamic treatment in combination with surgical antisepsis on bacterial skin colonization

- Skin swabs:
  - o Bacterial growth, density, and species before and immediately after PTD with standard bacterial cultures, MALDI-TOF for bacterial identification, semiquantitative amount of bacteria with dilution bacterial plates, molecular analysis using e.g RNA seq, whole genome sequencing
- Skin biopsies
  - o Changes of sebaceous and sweat glands after PDT (Histopathology with immunostaining)

**Outcome 2.** Long-term effect (1 and 3 weeks after PDT treatment) on bacterial skin colonization in the groin after photodynamic treatment

- Skin swabs:
  - o Bacterial growth, density, and species before and immediately after PTD with standard bacterial cultures, MALDI-TOF for bacterial identification, semiquantitative amount of bacteria with dilution bacterial plates, molecular analysis using e.g RNA seq, whole genome sequencing
- Skin biopsies
  - o Changes of sebaceous and sweat glands after PDT (Histopathology with immunostaining)

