#### **Study schedule:**

On day 0 with [name] and [name], a skin scraping of the groin will be performed and sent for microbiological culture. Then, 5% topical methyl aminolevulinate (MAL) as the photosensitizer will be applied for 3 hours under occlusion in the right groin of the patient. After the incubation, the photodynamic process will be started by irradiation of the area with 40J/cm^2 red light from a 633nm emitting LED during 13 minutes.

Immediately after the MAL-PDT, skin antisepsis will be performed. Antisepsis of the skin is performed with a povidone-iodine/alcohol solution (Betaseptic®, Mundipharma, Limburg, Germany) and repeated three times for a total duration of 3 minutes to imitate standard surgical antisepsis before a hip arthroplasty surgery. Skin scraping will be repeated after the 3rd antisepsis and 7 and 21 days later (study visit day 7 and 21) for bacterial cultures.

As a control group, we will take skin swabs before and after skin antisepsis without PDT in 10 participants.

On day 35 ( $\pm 7$  days) of the study, volunteers will be seen for the last study visit to document any adverse effects and to inform about the individual study result.

Substudy in 5 volunteers:

In the course of the study a total of three small skin biopsies are taken (3mm diameter each) from 5 volunteers. The time and locations of the performed biopsies will be

1. from the right groin immediately after the MAL-PDT or at day 7
2. from untreated control area in the left groin after the MAL-PDT (day 0 or 7)
3. from the MAL-PDT area on day 21 as the control after treatment.

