## 7.2 Administration of Study Intervention

### 7.2.1 Study Intervention

Details of study Intervention	Justification
1. Inguinal skin scraping before photodynamic treatment	Baseline microbiome data
2. Natural bacterial porphyrin fluorescence photography	Baseline fluorescence photography
3. Photosensitizer application, followed by fluorescence photography Photodynamic therapy (PHT) (1x) over 15 minutes at the dermatology ward	Treatment to kill bacteria and to reduce glands in order to reduce colonization bacteria
4. Skin antisepsis in the groin, skin scraping after antisepsis	To measure bacterial colonization to know the immediate effect of PDT
5. Punch biopsy  specimen of the MAL-PDT area (immediately after PDT) and of an untreated area as a control	To analyze size and structure of glands in the skin
6. Inguinal skin scraping and punch biopsy of the MAL-PDT area after 7 and 21 days	To measure bacterial colonization to know the long-term effect of PDT

 only in 5 participants

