## 8.2 Assessments of Outcomes

### 8.2.1 Assessment of Primary Outcome

What	When	How
Bacterial density and species of skin swabs and biopsies	Visit 2: immediate after intervention And Visit 3	Microbiological diagnostic methods (see below)
Histopathology	Visit 2 (day 0) and Visit 3 (after 21 days)	Routine dermatohistopathology

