**8.3.2 Visit 2 = Day 1 of the study**

On day 1 with [name] and [name], a skin scraping of the groin will be performed and sent for microbiological culture. Then, 5% topical methyl aminolevulinate (MAL) as the photosensitizer will be applied for 3 hours under occlusion in the right groin of the patient. After the incubation, the photodynamic process will be started by irradiation of the area with 40J/cm^2 red light from a 633nm emitting LED during 13 minutes.

Immediately after the MAL-PDT, skin antisepsis will be performed. Antisepsis of the skin is performed with a povidone-iodine/alcohol solution (Betaseptic®, Mundipharma, Limburg, Germany) and repeated three times for a total duration of 3 minutes to imitate standard surgical antisepsis before a hip arthroplasty surgery.

For all inguinal swabs, we will use the scratching method using a scalpel as already applied in a previous study (ethical approval BASEC-Nr 2016-01017). The swabs will be sent to the microbiology laboratory of the University of Zurich for bacterial analysis (analysis under supervision of Prof. [name]).

Skin biopsies will be done as a routine procedure at the Department of dermatology.

In short:

- Inguinal skin scraping before PDT
- Natural bacterial porphyrin fluorescence photography
- Study intervention: Photosensitizer application for 3 hours
- PDT for 15 minutes
- Inguinal skin scraping
- Skin antisepsis with povidone/iodine (3x times for 1 minute)
- Inguinal skin scraping
- Punch biopsies in 5 participants
- Documentation of adverse effects

Duration: 4 hours

Location: Department of dermatology, University Hospital Zurich

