**8.3.3 Visit 3 (day 7±3)**

Skin scraping after skin antisepsis will be repeated 7 days later and analyzed for bacterial cultures.

In short:

- Inguinal skin scraping

- Skin antisepsis
- Inguinal skin scraping
- Punch biopsies in 5 participants
- Documentation of adverse effects

**Duration:** 30 - 60 minutes

**Location:** Department of dermatology or Infectious Diseases, University Hospital Zurich

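### The sections give different scraping schedules, and none says whether the long-term primary outcome uses a sample taken before or after fresh antisepsis

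*Combined protocol and SAP*

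**What the plan says.** **Day 0.** Section 5.2 takes a scraping before PDT and then states "Skin scraping will be repeated after the 3rd antisepsis and 7 and 21 days later". Table 7.2.1 and the study plan table in 8.1 agree: one scraping before PDT, then "Skin antisepsis in the groin, skin scraping after antisepsis". The visit list in 8.3.2 puts a further scraping after PDT and ahead of the step "Skin antisepsis with povidone/iodine (3x times for 1 minute)", and another after that step. The paragraph on skin antisepsis in 8.1 places scrapings "before and after the 3rd antisepsis and 21 days later for bacterial cultures".

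**Days 7 and 21.** Section 5.2, table 7.2.1 and the 8.1 table have a single scraping at each visit and no antisepsis; the 8.1 table ticks antisepsis on day 0 only. Section 8.3.3 opens with "Skin scraping after skin antisepsis will be repeated 7 days later and analyzed for bacterial cultures", and 8.3.4 opens in the same way for day 21. The lists under both sentences read scraping, antisepsis, scraping. The 8.1 paragraph has no day-7 sample.

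**Outcome definitions.** Section 8.2.1 times the bacterial outcome at "Visit 2: immediate after intervention And Visit 3". Its histopathology row equates Visit 3 with 21 days, whereas 8.3.3 makes Visit 3 day 7. In 4.1, the heading of Outcome 2 refers to 1 and 3 weeks, but the bullet under it repeats the Outcome 1 text, "Bacterial growth, density, and species before and immediately after PTD with standard bacterial cultures". Table 7.2.1 gives the purpose of the post-antisepsis sample as "To measure bacterial colonization to know the immediate effect of PDT". Section 10.3.2 promises a descriptive comparison before and after PDT and names no sample.

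**The concern.** Both parts of the primary outcome are read from these scrapings, so the schedule decides what is being measured.

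On days 7 and 21, a scraping taken before antisepsis shows how far the skin has recolonised since PDT. One taken after a new antisepsis shows what survives that antisepsis. These are different quantities, and only the first is comparable with a baseline taken from undisinfected skin. Someone who follows the opening sentences of 8.3.3 and 8.3.4 together with the before/after comparison in 10.3.2 would compare disinfected with undisinfected skin and could credit the difference to PDT.

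On day 0, aim 1 in 3.1 concerns the effect of PDT as it stands before antisepsis, and table 7.2.1 uses the post-antisepsis sample to show the effect of PDT. With two scrapings, the change within a participant is the joint result of PDT and antisepsis. Staff working from different sections would also collect different data, and a day-0 sample that was not taken cannot be recovered.

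**Working it through.** **Step 1. Count scrapings per PDT participant in each section.**

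| Source | Day 0 | Day 7 | Day 21 | Total |
|---|---|---|---|---|
| 5.2; table 7.2.1; 8.1 table | 2 | 1 | 1 | 2 + 1 + 1 = 4 |
| 8.1 text, read literally | 2 | 0 | 1 | 2 + 0 + 1 = 3 |
| 8.1 text plus a pre-PDT baseline | 3 | 0 | 1 | 3 + 0 + 1 = 4 |
| 8.3.2 to 8.3.4 lists | 3 | 2 | 2 | 3 + 2 + 2 = 7 |

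For 10 PDT participants, 4 against 7 is 40 against 70 samples; for 20 it is 80 against 140. Both group sizes are shown because 7.1.1 gives PDT to 20 participants, while section 6 recruits 20 in all and 5.2 has 10 without PDT (20 − 10 = 10).

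**Step 2. Long-term contrast.** Let *P* be the lasting effect of PDT on day 7 or 21 and *A* the change produced by an antisepsis at that visit. Leave aside ordinary change over time.

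- Scraping before antisepsis, minus pre-PDT baseline: *P*.
- Scraping after antisepsis, minus pre-PDT baseline: *P* + *A*, if the two effects add.
- With *P* = 0, the first contrast is 0 and the second is *A*, a fall whenever antisepsis removes any bacteria.

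The documents give no figure for *A*, so the size of the spurious fall cannot be stated, only its direction.

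**Step 3. Day-0 contrasts.**

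- Two scrapings: after antisepsis minus before PDT gives PDT and antisepsis together. No within-person contrast gives PDT alone.
- Three scrapings (8.3.2): after PDT and before antisepsis, minus before PDT, gives PDT alone. After antisepsis minus before PDT gives the combined effect.
- Antisepsis-only group of 10 (5.2): PDT plus antisepsis against antisepsis alone gives the added effect of PDT between groups.

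**Step 4. Scale of the between-group route (illustration only).** The plan gives no rates and describes itself as descriptive. Assume a culture-positive share after antisepsis alone of 70%, borrowed from the cited study in 2.1 with seven of ten volunteers positive. That study sampled dermal tissue, so its use here is an assumption; the range taken is 50% to 90%. Power is the sum, over all pairs of positive counts in the two groups, of the product of the two binomial probabilities, counting only pairs with a two-sided Fisher p < 0.05. The control group is 10.

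| PDT group | Positive, antisepsis alone | Power if 0% / 10% / 20% are positive after PDT plus antisepsis |
|---|---|---|
| 10 | 50% | 62% / 30% / 13% |
| 10 | 70% | 95% / 67% / 43% |
| 10 | 90% | 100% / 96% / 84% |
| 20 | 70% | 99.8% / 92% / 73% |

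The route is therefore informative for large effects, less so if few controls are positive, and sensitive to whether 10 or 20 participants receive PDT.

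**The case against.** Several stronger readings are tempting, and the documents do not support them.

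- *PDT's effect cannot be told from that of antisepsis at all under 5.2.* A reader might infer this from the two-scraping schedule. Section 5.2 itself plans 10 participants with antisepsis and no PDT, and sections 2.5 and 6 add an external reference series. The limitation is only within participants. The control route is not secured, though: 7.1.2 says there is no control, the Synopsis sentence describing the group contradicts itself, and section 10 specifies no between-group contrast.
- *Outcome 1 requires a PDT-alone sample.* The Synopsis, 3.2 and the Outcome 1 heading in 4.1 consistently describe PDT together with antisepsis, and section 2.4 looks for sterile cultures after both. A post-antisepsis sample serves that outcome. The tension is with aim 1 in 3.1, the purpose given in table 7.2.1 and the Outcome 1 bullet.
- *Outcome 2 is defined as an immediate effect.* Its heading gives 1 and 3 weeks, and the Synopsis and 3.2 give days 7 and 21. The bullet looks like a copying slip, so the timing can be recovered. The antisepsis status of the sample cannot.
- *The 8.1 text calls for a sample between the second and third applications.* That is its literal sense, but it may mean before antisepsis and after its third application, which fits the 8.3.2 list.
- *Antisepsis on day 7 distorts the day-21 sample.* The order of events in 8.3 allows the question, but nothing in the documents shows carry-over.

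Two further points are fair. The visit number in 8.2.1 is probably left over from older numbering, since the table of contents still lists Visit 3 as day 21. And the flow charts are not available in the text reviewed and may mark the samples; they could not remove conflicts between the written sections and tables. The bias on days 7 and 21 is also conditional: every schedule except the 8.1 text (which lacks day 7) and the opening sentences of 8.3.3 and 8.3.4 includes an undisinfected scraping at both visits. What remains is that nobody is told to use it.

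**Conclusion.** The concern holds in limited form. The current text contains incompatible scraping schedules (4 against 7 per PDT participant), and the long-term primary outcome has no defined sample. If the post-antisepsis sample were used, the before/after comparison would be biased towards an apparent PDT effect. The direction follows from antisepsis removing some bacteria; the size is unknown. On day 0, the two-scraping version leaves PDT and antisepsis inseparable within participants, although a between-group comparison with 10 controls is possible if the plan commits to it. That the study is a descriptive pilot does not remove the problem, because a descriptive fall from baseline is what would be used to plan the later trial.

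**What to change.** 1. Reconcile 4.1, 5.2, 7.2.1, 8.1, 8.2.1 and 8.3 to one scraping schedule, with visit numbers as in 8.3 (day 7 = Visit 3, day 21 = Visit 4). State whether antisepsis is performed on days 7 and 21; that is for the sponsor to decide. Correct the bullet under Outcome 2.
2. In 10.3.2, name sample and comparator for each outcome:
   - long-term effect: the scraping taken before any antisepsis on days 7 and 21, against the pre-PDT baseline;
   - immediate combined effect: the post-antisepsis scraping on day 0, against the pre-PDT baseline, with PDT's added effect described against the antisepsis-only controls;
   - PDT alone: the scraping between PDT and antisepsis, against the pre-PDT baseline, if the 8.3.2 version is kept.
3. Bring 7.1.2 into line with the control group in 5.2, and write the control scrapings into the visit procedures, since 8.3 does not list them.

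The cost is a protocol amendment. Section 1.15 treats changes to endpoints, methods or analysis as substantial, so ethics committee approval may be needed. If the 8.3 schedule is adopted where 5.2 was being followed, it means up to 7 − 4 = 3 more scrapings per PDT participant (30 for 10, 60 for 20). Naming the analysis sample adds no procedure, because an undisinfected scraping on days 7 and 21 is in both the 5.2 schedule and the 8.3 lists.

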## Skin Biopsies

This will be done by the dermatologist Dr. med. [name] in 5 volunteers. A small piece of skin (3 mm) will be taken and transferred to a sterile tube for microbiological culture and histopathology. The skin biopsies will be taken after a local anesthesia. The wound will be closed with one stitch.

## 8.2 Assessments of Outcomes

### 8.2.1 Assessment of Primary Outcome

What	When	How
Bacterial density and species of skin swabs and biopsies	Visit 2: immediate after intervention And Visit 3	Microbiological diagnostic methods (see below)
Histopathology	Visit 2 (day 0) and Visit 3 (after 21 days)	Routine dermatohistopathology

## Microbiology

In short, the patient's sample swabs will be streaked out onto Columbia sheep blood agar plate without antibiotics (bioMérieux, Marly-l'Etoile, France), colistin-nalidixic acid (CNA) blood agar (bioMérieux) plate for aerobic cultivation and a Brucella plate (in-house sheep blood agar plates with hemin and vitamin K1) for anaerobic cultivation using GENbag (bioMérieux). Final identification will be done by matrix-assisted laser desorption ionization-time of flight mass spectrometry spectrometry (MALDI-TOF MS) using a Bruker MALDI Biotyper. The amount of bacteria will be semiquantitative described as +, ++, +++ based on growth on agar plates. All cultured microorganisms will be stored in skim milk at -80C° for potential subsequent analysis by whole genome sequencing for analyzing the secondary outcome.

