## 5 STUDY DESIGN AND COURSE OF STUDY

### 5.1 General Study Design and Justification of the Design

This is a pilotstudy of healthy volunteers, open label, and single center. If we see promising results in this pilotstudy, we will plan a prospective clinical trial in patients undergoing hip arthroplasty surgery.

[figure not shown]
The intended procedures are photodynamic treatment (PDT) on the first day followed by skin swabbing and biopsies for control of skin microbiome of treated area immediately after the PDT (outcome 1) and by controlling 3 weeks after PDT (outcome 2).

We think that this study design with healthy volunteers is adequate before starting a clinical trial.

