### 5.3 Methods of Minimizing Bias

Excluded bias in our collective

- No selected participants
- Both sex can be included
- Any age

Potential bias in our collective:

- Since we will search for healthy volunteers, the microbiome analysis might be slightly different to the population undergoing a hip arthroplasty surgery in an orthopedic hospital.

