### **Histopathology**

This part is to determine changes of eccrine gland lobules as a reduction in size, destruction or marked atrophy with molecular and immunofluorescence methods. In addition we will investigate the skin inflammation (type of immune cells, fibrosis).

The participants of this substudy have to sign a separate informed consent document for taking the skin biopsies.

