  - The collected project data may be subject to inspection by the CEC.

- Handling of isolated bacteria of the scrapped skin samples:  
The sub-cultivated bacterial samples will be stored and labeled with an encoded name at -80°C at the bacteriology laboratory of the Division of Infectious Diseases and Hospital Epidemiology (responsible [name]). The code for the bacterial strains with correspondence to patient data will be stored at the Investigator Site File.
- Handling of the skin tissue samples:
  - If the study patients agree, the remaining material from their skin samples will be kept for further research purposes in the Dermatological Biobank. If a study patient opposes the storage of skin sampling, they will be destroyed after the analyses planned as part of the study
  - Study patients receive a separate information leaflet for this purpose with the corresponding declaration of consent. The collection and storage of samples in the Dermatologische Biobank as well as the quality and safety standards are laid down in the regulations Dermatological Biobank USZ from the 1st of October 2017 (Dermatologische Biobank EK 647) and become in this research project accordingly implemented

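### Plate grades and any subjective histology reading are not masked to visit, side or group in this open-label pilot; neutral sample codes would reduce reader bias at small cost

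*Combined protocol and SAP*

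**What the plan says.** - **Design.** Section 5.1: "This is a pilotstudy of healthy volunteers, open label, and single center".
- **Density.** The Microbiology text under 8.2.1: "The amount of bacteria will be semiquantitative described as +, ++, +++ based on growth on agar plates". No colony-count boundaries, reader or reading rule are given. Section 4.1 speaks of "semiquantitative amount of bacteria with dilution bacterial plates", so dilution plates are named but the result is still a semiquantitative class.
- **Glands.** Sections 3.2 and 4.1 place gland changes under the primary outcome. The 8.2.1 table gives the method as "Routine dermatohistopathology". The Histopathology text says the aim is to determine "changes of eccrine gland lobules as a reduction in size, destruction or marked atrophy with molecular and immunofluorescence methods". Section 3.2 names gland number and size as the parameters.
- **Bias control.** Section 5.3 opens with "Excluded bias in our collective" and then lists participant selection, sex and age, followed by how far healthy volunteers represent arthroplasty patients. It does not mention the reading of samples.
- **Coding.** Section 12.2: "The sub-cultivated bacterial samples will be stored and labeled with an encoded name". It also has data encoded after the last visit. Section 1.13 uses participant numbers for confidentiality.
- **Checking.** Section 12.3 foresees regular control of results by an uninvolved microbiologist, still to be named.
- **Analysis.** Section 10.3.2 makes the primary analysis a descriptive before/after comparison, in at most 20 people (10.3.1).

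**The concern.** A three-step plus grade without stated boundaries leaves room for judgement on borderline plates. A reader who knows that a plate was taken after PDT may settle such a plate one grade lower, or a baseline plate one grade higher. The same holds for a slide known to come from the treated right groin rather than the untreated left.

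The primary result is a set of descriptive summaries in at most 20 people, with biopsies in 5. A few such readings would go straight into the reported result, and sampling error does not average them out because they lean one way. Sections 2.1 and 5.1 make promising results the basis for a trial in hip arthroplasty patients. Small numbers cannot be helped in a pilot, but this source of error largely can.

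**Working it through.** The plan states no figure on this point, so there is nothing to reproduce. The check has four parts.

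**1. Do the existing safeguards mask the reading?**

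| Safeguard | Where | Why it is not masking at reading |
|---|---|---|
| Participant code numbers | 1.13 | Serve confidentiality; nothing says visit, side or group is hidden |
| Encoded name on isolates | 12.2 | Applies to sub-cultivated isolates put into storage, not to the primary plate when it is graded; the content of the code is not described |
| Encoding of data | 12.2 | Takes place after the last visit |
| Uninvolved microbiologist | 12.3 | Not said to be masked or to re-grade plates |

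None of the four covers the moment when a plate or slide is read.

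**2. Which measures are exposed?**

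- Plate grade (+, ++, +++): exposed.
- Histology: exposed as far as it rests on judgement. The text also names molecular and immunofluorescence methods and counts and sizes of glands, without saying how these are read.
- Growth yes/no: less exposed.
- Species identification: not exposed ("Final identification will be done by matrix-assisted laser desorption ionization-time of flight mass spectrometry"). Sequencing (8.2.2): not exposed.

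**3. How large could the effect be?** All inputs here are assumptions.

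*Share with a reduction.* Shift = plates moved / plates read.
- 10 plates: 1/10 = 10 points; 2/10 = 20 points.
- 20 plates: 1/20 = 5 points; 2/20 = 10 points.

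These are upper limits. They require every borderline plate to move in the favourable direction and every move to turn no reduction into a reduction.

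*Tests.* A simulation with no true PDT effect (20,000 runs per scenario) used four levels (none, +, ++, +++). The level probabilities were either 25% each or 50/30/15/5%. Group sizes were 10 vs 10 and 20 vs 10. An unmasked reader lowers each positive PDT-group grade by one step with probability q. Expected mean shift = q × share of positive grades, for example 0.2 × 0.50 = 0.10 and 0.2 × 0.75 = 0.15. Tests were two-sided at 0.05.

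| q | Mean shift (grades) | Wilcoxon rank-sum false positives |
|---|---|---|
| 0 | 0 | 4.4–4.6% |
| 0.2 | 0.10–0.15 | 4.8–5.8% |
| 0.3 | 0.15–0.225 | 6.0–7.3% |
| 0.5 | 0.25–0.375 | 9.5–13.3% |

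Fisher's test on growth yes/no goes from 1.1–2.8% at q = 0 to 2.8–8.9% at q = 0.5. That assumes a + plate can be read as no growth, which is a severe assumption. The simulation compares two groups; the before/after comparison was not simulated.

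**4. How many samples would need a code?** Section 8.3 lists 3 scrapings at visit 2, 2 at visit 3 and 2 at visit 4, so 7 per PDT participant. Section 5.2 implies 2 per control participant.
- 10 PDT + 10 control: 7 × 10 + 2 × 10 = 90.
- 20 PDT, no control: 7 × 20 = 140.
- 20 PDT + 10 control: 7 × 20 + 2 × 10 = 160.

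The shorter schedule in 5.2 (4 scrapings per PDT participant) would give 60, 80 and 100. Biopsies: 3 × 5 = 15.

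**The case against.** The strongest reply has five parts.

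- **The grade is one of several parameters.** Section 3.2 also lists growth yes/no and identification. Section 2.4 ties the decision to go forward to sterile cultures. This stands. A reader might infer that a few grades decide whether the next trial goes ahead; section 2.4 does not support that, since its criterion is growth or no growth.
- **Bias is not shown.** The documents do not say that the reader sees visit or group, and section 13 assigns culture and identification to the Institute of Medical Microbiology rather than to the treating department. This stands in part. The text leaves bias possible, not demonstrated. But section 13 also has the infectious diseases division, which coordinates the study, generate microbiological data, enter data and analyse them, so organisational distance cannot be taken for masking.
- **Mild bias hardly affects the tests.** This stands: 4.8–5.8% at q = 0.2 against 4.4–4.6% without bias. It does not answer the point about the descriptive summaries, which are the planned primary analysis and still shift.
- **Group may not be a factor at all.** Section 5.2 describes 10 control participants without PDT, 7.1.1 lists PDT in 20, and 7.1.2 says there is no control intervention. These sections must be reconciled. Masking visit and side is useful either way.
- **Masking cannot be complete.** This stands. Sparse growth after antisepsis, or inflammation on a slide, may reveal where a sample came from. Nor does masking supply the missing boundaries between the grades.

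**Conclusion.** The point holds as a modest, avoidable weakness. The plate grade, and histology as far as it is subjective, are read without any stated masking of visit, side or group, and no other measure in the protocol fills that gap.

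The size of any bias is unknown. The 10 to 20 points are an upper limit on assumed inputs (1 to 2 borderline plates out of 10, all moved the favourable way), and half that if 20 plates are read. The simulation suggests that only strong reader bias would noticeably raise the false-positive rate at this sample size. The main risk is to the before/after summaries.

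Two stronger readings are tempting and not supported. One is that reader bias invalidates the pilot: growth yes/no, species identification and sequencing are little exposed or not exposed. The other is that coded labels would eliminate the bias: they would only reduce it.

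**What to change.** In 5.3 and 8.2.1, state that:

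1. Each swab tube and biopsy carries a neutral running number that shows neither visit, side nor group. Numbers should not follow the order of sampling within a participant, because section 8.3.2 has three scrapings on one day and consecutive numbers would show which came first.
2. Plates and slides are graded, and the grades locked, on a sheet or form keyed to that number before they are linked to the participant's eCRF. A separate form is needed because section 12.1.1 provides one eCRF per participant.
3. The link list is held by an existing team member who neither grades nor enters results. That excludes the study nurse and the doctoral student, who both enter data under 12.3.
4. If masking proves infeasible for some samples, this is stated and reported as a limitation.

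The documents give no costs. By count, the work is labels, one grading form and a carefully kept link list for roughly 90 to 160 swabs, depending on how 5.2, 7.1.1 and 7.1.2 are reconciled, and about 15 biopsies. No extra participant, visit, procedure or reader is needed, and treatment stays open label. The one new risk is a sample mix-up if the link list is poorly kept.
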